## Association between concomitant medication and adverse reactions

To examine the association between a concomitant medication and adverse reactions, patients with any adverse reaction will be summarized by concomitant medication in terms of n. For each patient, concomitant medications used after the last dose should be excluded from consideration.

## Adverse reactions in patients excluded from the SAS

Using the set of all CRF-collected patients, adverse reactions in patients excluded from the SAS will be tabulated. In addition, patients with an adverse reaction will be counted for each SOC and PT.

#### 8.2.3.2. Adverse events

#### All adverse events

The number and proportion of patients with adverse events will be tabulated by SOC and PT.

#### Adverse events by serious/non-serious

The number and proportion of patients with serious adverse events will be tabulated by SOC and PT by causal relationship. Non-serious adverse events will also be tabulated in the same manner.

#### Deaths

For patients recorded as "death," date of registration, age at the time of registration, experience of treatment with this drug, target disease and onset timing, mutant genotype, Karnofsky performance status, classification of accumulated cases/non-accumulated cases, presence or absence of liver transplant, NIS at baseline, QOL-DN, ambulatory status, name of adverse event, date of onset of adverse event, and causal

PFIZER CONFIDENTIAL Page 28 relationship of adverse event to this drug will be shown in a list. The number and proportion of patients will be tabulated for the grade of serious adverse events.

#### Adverse events leading to discontinuation

Adverse events leading to treatment discontinuation will be tabulated by SOC and PT.

## 8.2.3.3. Subgroup analyses

The number and proportion of patients who experienced at least 1 adverse reaction will be tabulated by factor specified in Section 5.4. The evaluation specified in Section 8.1.3 will be performed to evaluate the relationship between patient characteristics and the onset of adverse reactions. In the calculation of risk ratio, the categories to be used as the reference are underlined.

Hepatotoxicity will also be evaluated in the same manner as above if it occurs at a sufficient incidence in the evaluation.

The evaluation specified in Section 8.1.3 will be performed for infection with the presence or absence of liver transplant as a factor.

The number and proportion of patients with adverse reactions will be tabulated by SOC and PT by history of liver transplant. Events related to blood disorder in particular will be examined based on the tabulation results

The number and proportion of patients with adverse reactions will be tabulated by SOC and PT for each category of age [< 15 years,  $\ge$  15 to < 65 years,  $\ge$  65 years], hepatic impairment [Yes, No], and renal impairment [Yes, No]. The number and proportion of patients with adverse reactions in the subgroup of hepatic impairment [severe] will also be tabulated by SOC and PT.

#### CCI

#### 8.2.4. Efficacy analyses

#### 8.2.4.1. Time course of NIS

For each of the total score, NIS-LL score, and NIS-UL score, the following analyses will be performed:

- 1. Summary statistics at each evaluation time point (see A1.1) will be calculated.
- 2. Summary statistics of the change from before the start of treatment with this drug to each evaluation time point after the start of treatment with this drug will be calculated.

## 8.2.4.2. Time course of QOL-DN

The following analyses will be performed for TQOL score, physical function/large nerve fiber disorder score, activities of daily living score, symptom score, small nerve fiber disorder score, and autonomic neuropathy score:

- 1. Summary statistics at each evaluation time point (see A1.1) will be calculated.
- 2. Summary statistics of the change from before the start of treatment with this drug to each evaluation time point after the start of treatment with this drug will be calculated.

## 8.2.4.3. Time course of mBMI

Summary statistics of mBMI at each evaluation time point (See A1.2) will be calculated.

Summary statistics of the change from before the start of treatment with this drug to each evaluation time point after the start of treatment with this drug will be calculated in the same manner.

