7.2.4. Observation period

3 years from the first day of treatment with this drug (156 weeks) However, the observation period for patients who started to receive this drug after May 2018 will be 1.5 years (78 weeks).

> Pfizer Confidential Page 12 of 37

If the treatment with this drug is discontinued during the observation period, the observation period will be until the day of discontinuation. If the dose of this drug is changed for the treatment of ATTR-CM, the observation period will be up to the date of last dose of 20 mg.

This study will be conducted using booklet type CRF.

The safety and efficacy assessments will be performed at the first visit (including the end date of the observation period) on or after the end date of the observation period (day of discontinuation if the treatment is discontinued during the observation period or date of the last dose of 20 mg if the dose was changed for the treatment of ATTR-CM). However, if a subject is lost to follow-up halfway through, the safety and efficacy assessments will be performed using the information on the last visit date.

Booklet No.	Observation period	
Booklet 1	First day of treatment to Week 78 (1.5 years)	
Booklet 2	Week 79 to Week 156 (3 years)	

7.3. Registration items and study items This study will be conducted according to the following schedule of observation.

Table 1. Schedule of observation

			Booklet 1		Book	det 2
Item	Registr ation form	At start of the study	Week 52 (1 year)	Week 78 (1.5 years)	Week 104 (2 years)	Week 156 (3 years)
Information to identify the subject			-	-	-	-
First day of treatment with this drug			-	-	-	-
Presence or absence of having received/used this drug at other sites, and if Yes, patient's duration of treatment	•					
THAOS registration status/THAOS registration ID						
State of concurrent medical examination	-					→
Background variables	-		-	-	-	-
History of previous treatment drugs for the targeted disease	-	•	-	-	-	-
Targeted drug use record	-	•				>
Concomitant therapy (drug therapy/ non-drug therapy)	-	•				
General tests (height, body weight, pulse, blood pressure)	-	•				
Clinical laboratory tests	-	•				→
Plasma concentration of tafamidis (to be performed only for patients with severe hepatic impairment)	-					•
Cardiovascular evaluation (ECG, echocardiography)	-					
Assessment of neurological function (NIS)	-		-		-	
Quality of Life (QOL-DN)	-		-		-	
Ambulatory state	-		-		-	

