			10.3.2. Analysis of repeated measures data
			• Added a sample SAS code to show how the percent
			change described in Section 8.2.4.8 will be
			calculated.
			Other: Minor corrections
			• Made a terminological change from "study period"
			to "observation period".
			• In "Evaluation of survival time", Section 6.2,
			clarified the explanation of when survival will be
			determined.
10.0	13-Mar-2023	PPD	5.4. Subgroups
			• Changed the reference category for pretreatments
			and concomitant medications to "absent".
			• Identified the pretreatments and concomitant
			medications for which subgroup analysis will be
			performed.

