## 8. STATISTICAL METHODS AND ANALYSES

#### 8.1. Statistical Methods

#### 8.1.1. Continuous variables

For continuous variables, summary statistics (n, mean, standard deviation [SD], median, maximum, minimum) will be presented.

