#### 8.1.4. Repeatedly measured variables

Mixed effect modeling will be used to analyze repeatedly measured objective variables. The model will include fixed effects of baseline value (included only when the variable represents a change) and time of measurement, and a random effect of patient, with unstructured dispersion being assumed. The least square mean and its standard error at each time of measurement will be determined for each objective variable.

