## 8.2.4.5. Time course of neurological assessment

[figure not shown]
Summary statistics of the measured values of the total score, motor function score, tendon reflex score, and sensation score at each evaluation time point (see A1.3) will be calculated.

Summary statistics of the change from before the start of treatment with this drug to each evaluation time point after the start of treatment with this drug will be calculated in the same manner.

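### The legible efficacy time courses, mBMI most clearly, average whoever is observed at each visit, so movement in the mean toward Week 156 mixes change in patients with change in who is measured.

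*SAP*

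**What the plan says.** **Analyses.** SAP 8.2.4.3 (mBMI): "Summary statistics of mBMI at each evaluation time point (See A1.2) will be calculated", with changes from baseline handled likewise. SAP 8.2.4.5 (neurological assessment) plans "Summary statistics of the measured values of the total score, motor function score, tendon reflex score, and sensation score at each evaluation time point". SAP 8.2.4.1 (NIS) plans "Summary statistics at each evaluation time point (see A1.1) will be calculated" and "Summary statistics of the change from before the start of treatment with this drug to each evaluation time point after the start of treatment"; 8.2.4.2 (QOL-DN) has the same two steps. SAP 8.1.1 defines the content: "summary statistics (n, mean, standard deviation [SD], median, maximum, minimum) will be presented".

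**Follow-up.** Protocol 7.2.4 sets 156 weeks, but "the observation period for patients who started to receive this drug after May 2018 will be 1.5 years (78 weeks"). Observation also ends on the day of discontinuation, or at the last 20 mg dose if the dose is changed for ATTR-CM.

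**Windows (SAP Appendix 1).** mBMI at Week 156 takes Weeks 144 to 169. The neurological assessment has Weeks 52, 104 and 156 and no Week 78. For NIS and QOL-DN, the Week 156 window is any record after Week 104, with no upper limit.

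**Model.** SAP 8.1.4: "Mixed effect modeling will be used to analyze repeatedly measured objective variables", with least-squares means at each time. No legible efficacy section calls on it. The revision history cites "10.3.2. Analysis of repeated measures data" and has a redacted entry for 8.2.4.1 and 8.2.4.2; that content cannot be seen.

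**The concern.** Long-term efficacy is a stated objective, the final analysis supports reexamination, and there is no control group (Protocol 7.9). The course over time is therefore the main efficacy evidence, and a reader will take a flat or moving mean as stabilisation or progression. If late starters leave the table by plan, and others leave because they stop treatment or die, the mean can move with no patient changing. If worsening patients leave, Week 156 looks better than it should.

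Nothing legible separates the two effects:
- SAP 8.2.1 counts patients by planned observation time, but only in the safety set.
- Planned observation length is not a factor in SAP 5.4, and the subgroup summaries in 8.2.4.7 cover NIS-LL and TQOL, not mBMI.
- Duration of treatment cannot stand in for it. SAP 8.2.2 codes anyone still on treatment at the end of observation as more than 156 weeks. Read literally, that puts 78-week completers with the longest-treated patients.
- SAP section 7 has no rule for a missed visit.

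**Working it through.** **1. The plan's own size figure.** Prevalence × population: 0.87 × 127.54 = 110.96 and 1.1 × 127.54 = 140.29. This reproduces the stated 111 to 140 patients.

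**2. Share s of patients in the 78-week cohort.** The documents give none. Registration runs November 2013 to November 2019 (72 months), and about the last 18 months feed this cohort. Uniform accrual gives s = 18/72 = 25%. In an all-cases survey with retrospective capture, existing patients may register early, which lowers s. I use 5% to 25%.

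**3. Patients left at Week 156 by design alone, N(1 − s).**

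| s | N = 111 | N = 140 |
|---|---|---|
| 5% | 105 | 133 |
| 10% | 100 | 126 |
| 25% | 83 | 105 |

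With an assumed discontinuation d per 78 weeks, the fraction of Week 78 patients absent at Week 156 is 1 − (1 − s)(1 − d). For d = 10% this is 14.5% (s = 5%) to 32.5% (s = 25%); for d = 20% it is 24% to 40%.

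**4. Artefact in raw means.** Let the 156-week cohort have mean m at Week 78 and the 78-week cohort m + δ, with no true change afterwards. The Week 78 mean is (1 − s)m + s(m + δ) = m + sδ and the Week 156 mean is m, so the step is −sδ. Its size in SD units, for assumed δ:

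| s | δ = 0.2 | δ = 0.5 | δ = 1.0 |
|---|---|---|---|
| 5% | 0.01 | 0.025 | 0.05 |
| 10% | 0.02 | 0.05 | 0.10 |
| 25% | 0.05 | 0.125 | 0.25 |

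It is zero if δ = 0. SD units are used because the documents give no mean or SD for any score.

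**5. Change from baseline.** Put mean changes c and c + γ in place of the levels; the artefact becomes −sγ. A constant level gap between cohorts cancels. Only a different rate of change, or dropout that depends on progression, leaves an error.

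**6. Simulated check of remedies.** Assumptions: 140 patients, 4,000 runs, correlation 0.7, no true mean change from Week 78 to Week 156. Where dropout is included, its probability rises with the Week 78 value (about 15% at the 156-week cohort's mean). Steps in SD units:

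| Scenario | Raw | Same patients at both visits | Unstructured likelihood model, no cohort term |
|---|---|---|---|
| s = 25%, δ = 0.5 | −0.124 | 0.000 | −0.038 |
| s = 10%, δ = 0.5 | −0.050 | 0.001 | −0.014 |
| s = 25%, δ = 0 | 0.000 | 0.000 | 0.000 |
| Dropout only | −0.090 | +0.042 | 0.003 |
| s = 25%, δ = 0.5, with dropout | −0.218 | +0.038 | −0.039 |

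The first row agrees with 0.25 × 0.5 = 0.125. The same-patient summary removes the cohort artefact. The model removes about 70% of it (1 − 0.038/0.124). With dropout only, the model does best, but that dropout depends solely on an observed value, which favours it.

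**The case against.** This is a descriptive survey: SAP 4.1 and 4.2 set no hypothesis or decision rule, and no Week 78 against Week 156 contrast is planned. Every table reports n, discontinuations are tabulated by timing and reason, individual efficacy values are listed, and change from baseline is within patient. All of that stands, and it limits the harm. But n shows that the set shrank, not who left, and a mean of within-patient changes is still a mean over a changing set.

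A reader might infer that the two visits compare different patients. They do not: the Week 156 set is largely a subset of the Week 78 set.

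A reader might also infer that every score is affected alike. For NIS and QOL-DN, an assessment is scheduled at discontinuation, and one made after Week 104 falls in the Week 156 window. A late closing visit or linked data from another site could also place a 78-week patient there, so loss is smaller. For the neurological assessment the affected steps are those toward Weeks 104 and 156. A 78-week patient's closing assessment may fall in the Week 52 window (Weeks 4 to 78) or the Week 104 window (Weeks 79 to 130).

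Finally, a reader might infer that the plan has no repeated-measures model. SAP 8.1.4 sets one out, and redaction prevents judging whether NIS and QOL-DN use it. What can be said is that the legible 8.2.4.3 and 8.2.4.5 do not call it.

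**Conclusion.** The point holds for mBMI as written, for the neurological scores toward Weeks 104 and 156, and with less force for the legible NIS and QOL-DN steps. The Week 78 to Week 156 movement in raw mBMI means cannot be read as patient change alone.

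The size is not known from the documents. It is 0.01 to 0.25 SD in raw means if s is 5% to 25% and δ is 0.2 to 1.0 SD, and zero if the cohorts are alike. The upper figure needs both uniform accrual and a full 1 SD gap. A claim that the means will shift by a given number of score points, or that change from baseline is distorted by a level gap alone, is not supported. The direction is also open: it depends on how late starters differ, and on mBMI a fall, not a rise, is worsening.

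**What to change.** In SAP 8.2.4.1 to 8.2.4.3 and 8.2.4.5:

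1. Present values and changes by planned observation length (78 or 156 weeks), with n at each time point.
2. For the 156-week cohort, add summaries in the same patients observed at the compared visits: Weeks 78 and 156 for mBMI, NIS and QOL-DN; Weeks 52, 104 and 156 for the neurological assessment.
3. Show baseline values of patients with and without a Week 156 value.
4. As a supporting analysis, state that the 8.1.4 model is applied to mBMI and the neurological scores (and to NIS and QOL-DN if not already done), with planned observation length as a term.

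The cost is SAP wording and a few more tables; no new data are needed. Neither remedy is complete. The same-patient summary can still be biased by informative dropout (about +0.04 SD in the check). The model assumes data are missing at random, which is doubtful after death, so it should support the tables and not replace them.

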# **8.2.4.4.** Time course of ambulatory status (ambulatory ability scale in polyneuropathy disability score)

The number and proportion of patients will be calculated with ambulatory status before the start of treatment with this drug on the side of the table and ambulatory status at each evaluation time point after the start of treatment with this drug (see A1.1) on the top of the table.

## 8.2.4.5. Time course of neurological assessment

[figure not shown]
Summary statistics of the measured values of the total score, motor function score, tendon reflex score, and sensation score at each evaluation time point (see A1.3) will be calculated.

Summary statistics of the change from before the start of treatment with this drug to each evaluation time point after the start of treatment with this drug will be calculated in the same manner.

## 8.2.4.6. Evaluation of survival time

Each time to each event  $(2 \times 2)$  noted in the evaluation of survival time in Section 6.2 will be analyzed as described in Section 8.1.5. Survival rates will also be calculated at 1.5 and 3 years for the time from the start of treatment to the event and at 10 and 20 years for the time from FAP onset to the event (enter NA if not estimable). When death related to FAP is an event, other deaths will be right-censored.

[figure not shown]
The outline of how to handle cases at the time of analysis in the evaluation of survival time is shown below.

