#### 5. ANALYSIS SETS

#### 5.1. Safety Analysis Set

Safety analysis will be performed using the safety analysis set (SAS) that consists of all registered patients who had their CRF collected and received at least one dose of this drug.

Patients who meet any of the criteria below, however, should be excluded from the SAS:

- Contract deficiency
- Contract violation
- Contract withdrawal
- Registration violation
- No information recorded on adverse events (Patients who had no record or made no visit even after reinvestigation was conducted because there was no record of AEs or of lack of AEs)

Although patients will not be excluded from the SAS just because reinvestigation could not be conducted, patients whose all records concerning administration of this drug or safety information could not be reinvestigated will be excluded from the SAS according to the criterion above.

Patients with iatrogenic TTR-FAP in whom TTR-FAP developed after liver transplantation from a donor with TTR-FAP (domino liver transplantation) will be included in this study. Patients registered for a non-target disease (e.g., cardiac amyloidosis) will also be included in the SAS.

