Survival time will be evaluated by setting death as the event of interest. For patients who complete the study, survival status will be determined on the first follow-up date exceeding 3 years after the start of treatment with this drug at the own site. In the case of death, information on the cause, i.e., whether the death is due to TTR-FAP or to another cause (including unknown) will also be collected. *For patients who started the treatment with this drug after May 2018 (1.5-year observation period), their survival should be confirmed using the attached CRF* on the first follow-up date exceeding *1.5 years after the start of treatment at the own site.* 

The following two kinds of event will be evaluated:

- Death from any cause
- FAP-related death (Death from TTR-FAP is set as the event of interest. Death with missing cause will
  not be regarded as an event of interest.)

Time to event will be evaluated with respect to the following two kinds of time:

- Time from start of treatment to event
- Time from onset of FAP to event

CC				
I				
l				

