#### 8.1.5. Time (to event) data

For time data containing right-censored data, Kaplan-Meier's method will be used to determine the median, 1st quartile, and 3rd quartile. Kaplan-Meier plots will also be presented, as necessary.

For time data containing interval censored data, the EMICM algorithm will be used to determine the median, 1st quartile, and 3rd quartile. Estimated survival plots will also be presented, as necessary. A reference program is shown in Section 10.3.1.

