#### 8.2. Statistical Analyses

#### 8.2.1. Description of patients

#### **Combination clinical practice**

Given the nature of this disease as a rare disease, patients may be treated (or receive prescriptions of this drug) at multiple sites during the observation period (combination clinical practice). For possible patients

PFIZER CONFIDENTIAL Page 23 with combination clinical practice, identification will be determined at a case conference using information on birthdate, sex, mutant genotype, and names of combination practice sites or sites after patient transfer. In principle, data at the site with earlier date of treatment initiation will be adopted for the analysis of patient characteristics. All data after the start of treatment for an identical patient will be combined and handled using this start date of treatment as the origin (data linkage).

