## 10.2.3. Neurological Assessment

1	Motor	Elbow flexion
2	Motor	Brachioradialis
3	Motor	Elbow extension
4	Motor	Wrist flexion
5	Motor	Wrist extension
6	Motor	Finger flexion
7	Motor	Finger spread
8	Motor	Thumb abduction
9	Motor	Hip flexion
10	Motor	Hip extension
11	Motor	Knee flexion
12	Motor	Knee extension
13	Motor	Ankle dorsiflexors
14	Motor	Ankle plantar flexors
15	Motor	Toe extension
16	Motor	Toe flexors
1	Reflexes	Biceps brachii

2	Reflexes	Triceps brachii
3	Reflexes	Brachioradialis
4	Reflexes	Quadriceps femoris
5	Reflexes	Triceps surae
1	Light Touch	Fingers
2	Light Touch	Hand
3	Light Touch	Lower arm
4	Light Touch	Upper arm
5	Light Touch	Thigh
6	Light Touch	Knee
7	Light Touch	Mid-calf
8	Light Touch	Lower-calf
9	Light Touch	Mid-foot
10	Light Touch	Тое
11	Light Touch	Trunk
1	Pin Prick	Fingers
2	Pin Prick	Hand
3	Pin Prick	Lower arm
4	Pin Prick	Upper arm
5	Pin Prick	Thigh
6	Pin Prick	Knee
7	Pin Prick	Mid-calf
8	Pin Prick	Lower-calf
9	Pin Prick	Mid-foot
10	Pin Prick	Тое
11	Pin Prick	Trunk
1	Vibration	Wrist
2	Vibration	Thumb
3	Vibration	Hip
4	Vibration	Knee
5	Vibration	Ankle
6	Vibration	Тое
1	Position Sense	Wrist
2	Position Sense	Fingers
3	Position Sense	Ankle
4	Position Sense	Тое

CCI

Proc Iclifetest Data=data Method= EMICM Plots=survival Outsurv=out;

CCI				
		_

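### Survival from FAP onset is planned with no stated entry time, so years lived before the first dose count as risk time and the onset-scale survival figures come out too high

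*SAP*

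**What the plan says.** SAP 6.2 defines two events (death from any cause, FAP-related death) on two time scales, one of them "Time from onset of FAP to event". SAP 8.2.4.6 sends all four combinations to SAP 8.1.5 and adds survival rates "at 10 and 20 years for the time from FAP onset to the event", with NA where not estimable.

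SAP 8.1.5 gives two methods:
- "For time data containing right-censored data, Kaplan-Meier's method will be used to determine the median, 1st quartile, and 3rd quartile"
- "For time data containing interval censored data, the EMICM algorithm will be used to determine the median, 1st quartile, and 3rd quartile"

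Neither sentence names an entry time, left truncation or a delayed-entry risk set. The one legible line of the reference program in the SAP appendices, "Proc Iclifetest Data=data Method= EMICM Plots=survival Outsurv=out", has no entry variable; the code around it is blacked out.

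The analysis population is built from patients who "received at least one dose of this drug" (SAP 5.1). Survival status is taken at the first follow-up past 3 years from the start of treatment, or past 1.5 years for starts after May 2018 (SAP 6.2; protocol 7.3.2.13). Records from several sites are linked and "handled using this start date of treatment as the origin" (SAP 8.2.1).

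SAP 8.2.4.6 also announces an outline: "The outline of how to handle cases at the time of analysis in the evaluation of survival time is shown below". That figure is not in the text available for review.

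**The concern.** Someone whose symptoms began eight years before the first dose could not have died in those eight years and still be in the study. Anyone who did die between onset and first dose is absent. A Kaplan-Meier curve that starts everyone at onset nevertheless keeps that patient in the risk set for all eight years. The denominators are too large, the estimated hazard is too small, and survival looks longer than it is. EMICM without a truncation time has the same fault.

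Survival time is listed as an efficacy endpoint in SAP 5.2, the study has no control group (protocol 7.9), and the final analysis supports the reexamination application (SAP 3). The only survival figure in the documents is about 10 years after onset, given for the accumulated area (protocol 5). A reader could set the onset-scale result beside it and see a benefit where there is none.

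**Working it through.** **Inputs from the documents.** Follow-up is 3 years, or 1.5 years for late starters. Survival after onset is about 10 years for the accumulated area, used here as the true median. The size estimate is prevalence times population: 0.87 × 127.54 = 110.96 and 1.1 × 127.54 = 140.29, which reproduces the stated 111 to 140. Cohorts of 125 or 130 are used below. The documents give no expected survival rate for this study to reproduce.

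**Assumptions.** Disease duration at first dose is collected but no distribution is given, so it is varied. The drug is taken to have no effect on survival. Survival from onset is Weibull with median 10 years and shape 1 to 3.

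**Direction.** Kaplan-Meier is S(t) = Π(1 − dᵢ/nᵢ). The deaths dᵢ are the same with or without delayed entry. The ordinary nᵢ counts everyone with exit ≥ tᵢ; the delayed-entry nᵢ counts only those with entry < tᵢ ≤ exit. The ordinary nᵢ is never smaller, so the ordinary curve is never lower. In 4,000 simulated cohorts of 125 there were 0 exceptions.

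**Who can be observed.** With 3-year follow-up, being under observation at year 10 needs a first dose at least 10 − 3 = 7 years after onset; at year 20, 20 − 3 = 17 years. With 1.5 years the figures are 8.5 and 18.5.

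**Size, one case by hand.** Take shape 1, so λ = ln 2/10 = 0.0693. Let the onset-to-dose gap be exponential with mean 5 years before selection, and follow-up 3 years.
- Selection on survival to first dose gives an enrolled gap with rate a = 1/5 + 0.0693 = 0.2693, i.e. mean 3.7 years.
- From year 3 on, the ratio of patients under observation to patients not yet entered is K = (0.2693/0.2)(e^0.6 − 1) = 1.107. The share of the ordinary risk set truly under observation is 1.107/2.107 = 0.525.
- Over years 0-3 that share integrates to 0.904.
- Planned S(10) → exp[−0.0693 × (0.904 + 7 × 0.525)] = 0.728, true 0.50.
- Planned S(20) → exp[−0.0693 × (0.904 + 17 × 0.525)] = 0.506, true 0.25.
- Planned median = 3 + (10 − 0.904)/0.525 = 20.3 years, true 10.

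Simulation of the same case with 100,000 patients gave 0.733, 0.507 and 20.5 years. With 125 patients the mean S(10) was 0.728 planned and 0.501 with delayed entry.

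**Other durations (simulation, shape 1, 100,000 patients, 3-year follow-up).** Gaps are before selection.

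| Gap | Planned S10 | Delayed-entry S10 | Planned S20 | Delayed-entry S20 |
|---|---|---|---|---|
| Exponential, mean 3 | 0.663 | 0.499 | 0.419 | 0.250 |
| Exponential, mean 5 | 0.733 | 0.511 | 0.507 | 0.254 |
| Exponential, mean 10 | 0.801 | 0.500 | 0.618 | 0.250 |
| Uniform 0-25 | 0.875 | 0.496 | 0.712 | 0.252 |

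With shape 2 (true S20 = 0.5^4 = 0.063), mean gap 3 gives S10 0.623 and S20 0.123; mean gap 10 gives 0.735 and 0.236. With mean gap 1 and shape 1, S10 is 0.576 planned against 0.529 with delayed entry. If everyone entered at onset, the two estimators would coincide.

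**Wider grid (shapes 1 to 3, 3- and 1.5-year follow-up mixed), large-sample planned S10 against a true 50%, by mean duration at first dose:**
- about 1 year: 50-55%
- 1.8-2.0 years: 53-62%
- 2.5-2.8 years: 58-67%
- 3.4-6.3 years: 64-82%

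Spreading onset evenly over calendar time from 1975, 1990 or 2000 to 2019 gives 73-88%. The planned median is 10-14 years at mean duration 1.8-2.0 and 11-27 years at 3.4-6.3.

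**NA entries.** At n = 130 and mean duration 1 year, the 10-year rate is NA in about 95% of cohorts. Below 2 years, the 20-year rate is NA in at least 99%.

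**Interval-censored branch.** With 30% of deaths of unknown date, the untruncated estimate of S10 is 55-81% and the left-truncated one 45-51%.

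**The case against.** The strongest point is the missing outline. A figure on how cases are handled in the survival analysis is a natural home for an entry rule, and the reference code is mostly blacked out. That stands: the finding is conditional on the unseen material holding no such rule. But 8.1.5, which defines the estimators, is legible and names plain methods.

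Second, the output is secondary. Protocol 7.3.2.11 does not list survival among its ten effectiveness items, protocol 7.7 plans survival analysis only up to 3 years after treatment start, and SAP 4.1 and 4.2 set no hypothesis or decision rule. No legible text plans a comparison with the 10-year figure. This limits the severity, not the error.

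Third, the size rests on assumed durations, hazard shape and true median. The cohort is also wider than the accumulated area, so 50% at 10 years is itself an assumption. All of this stands; only the direction is free of these choices.

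Fourth, the 10-year rate is a product over all earlier death times, so patients with short durations contribute too. That is correct; only the late part of the curve rests on late starters.

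Fifth, delayed entry needs treatment start to be independent of prognosis. One test broke this: half the patients with median 20 years and mean gap 8, half with median 7 and mean gap 2. Delayed entry gave 0.556 at 10 years (true 0.545) and 0.348 at 20 years (true 0.268). The planned estimator gave 0.766 and 0.637. The remedy is imperfect there, but much closer to the truth.

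**Conclusion.** The concern holds on the legible text. As written, the onset-scale median and the 10- and 20-year rates overstate survival, for all-cause and for FAP-related death. The direction follows from the risk sets. The size depends on disease duration at first dose: near zero to 5 points at 10 years when mean duration is about 1 year, and 14 to 32 points when it is 3.4-6.3 years (64-82% less 50%). At 20 years, in scenarios where mean duration is 3.4-6.3 years or onset is spread from 1975 or 1990, the excess runs from about 1 to 51 points, largest under a constant hazard. These figures assume no drug effect and a true median of 10 years.

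The NA rule gives little protection: the rates are mostly NA where the bias is small and reportable where it is large. This should be fixed before the final analysis, but it is not critical, because the output is descriptive and the start-of-treatment analyses do not share the fault.

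**What to change.** First check the outline in SAP 8.2.4.6. If it sets an entry rule, repeat that rule in 8.1.5. If not:

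- Use a left-truncated product-limit estimator for both onset-scale analyses. Time is years since onset; entry is the later of onset and the first day of treatment (protocol 7.3.1, or the linked start date of SAP 8.2.1); exit is death or censoring.
- For deaths of unknown date, use an interval-censored estimator that accepts left truncation, or a stated date rule such as the midpoint with sensitivity analyses at both ends. In the test case of mean gap 5 and shape 1.5, these two gave 0.501 and 0.502 at 10 years, against 0.709 untruncated.
- Report the number actually under observation at 10 and 20 years. Where early risk sets are sparse, report survival conditional on being alive at a stated time since onset, with NA if not estimable.
- State the assumption that timing of treatment start is independent of prognosis.
- Leave the start-of-treatment analyses as they are.

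**Cost.** SAP wording and some programming; onset timing and first treatment day are already collected. With n = 130 and mean duration 3.4 years or more, the standard deviation of the 10-year rate rises from about 0.03-0.09 to 0.09-0.11. About 8-15 patients are under observation at 10 years and at most about 6 at 20 years, so more 20-year entries will be NA. At mean duration about 1.8 years, delayed entry averages 51-55% with standard deviation 0.15-0.20. The reported survival will also be less favourable.
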